8.3.6.3 Modified Physical and Neurological Examination

A modified physical examination, including neurological and excluding genital/rectal examinations, will be performed. The examination should include evaluation of height (m; at Screening/Visit 1 only); body weight (kg); waist circumference (cm); appearance and skin; head and neck; eyes, ears, nose, and throat; chest and lungs; heart; abdomen; and extremities. Neurological findings will also be recorded. All physical examination findings must be documented in the patient's study chart and also recorded in the eCRF.

9 STATISTICAL CONSIDERATIONS

A statistical analysis plan (SAP) will be finalized prior to unblinding the patients' treatment assignments and will provide further details regarding the definition of analysis endpoints and analysis methodology to address all study objectives. Changes made to the data analysis methods as described in the protocol will be documented in the SAP and will not necessitate a protocol amendment. All departures from the statistical analyses described in the approved protocol, whether made before or after unblinding, will be documented, and justified in the final clinical study report.

The study randomized 100 patients with Bipolar Disorder (Bipolar I or Bipolar II) before Amendment 2.0 (dated 02 Nov 2020). The efficacy data of these 100 patients will be combined with those of patients with Bipolar Disorder enrolled after Amendment 2.0 as a separate analysis.

Table 9-1 presents an overview of the statistical data analyses planned for all patients enrolled in the study.

Table 9-1: Overview of Statistical Data Analyses

	Patients	Patients Randomized after Protocol Amendment 2.0			All Bipolar Patients	All Patients
Analysis	Randomized before Protocol Amendment 2.0	Bipolar Disorder with Mixed Features	MDD with Mixed Features	All Patients Randomized after Protocol Amendment 2.0	(randomized before or after Amendment 2.0)	randomized before or after Amendment 2.0
Patient Disposition	Yes	Yes	Yes	Yes	Yes	Yes
Protocol Deviation	Yes	Yes	Yes	Yes		Yes
Demographic and baseline characteristics	Yes	Yes	Yes	Yes	Yes	Yes
Bipolar Diagnosis, Psychiatric Diagnosis and History	Yes	Yes	Yes	Yes	_	_
Medical History	Yes	Yes	Yes	Yes	—	—
Prior/Concomitant Medication	Yes	Yes	Yes	Yes	—	_
Exposure/ Compliance	Yes	Yes	Yes	Yes	Yes	Yes
Primary and Key Secondary Efficacy	Yes ¹	Yes	Yes	Yes	Yes	Yes
AE	Yes	Yes	Yes	Yes	Yes	Yes
Labs	—	Yes	Yes	Yes	Yes	Yes
Vital Signs		Yes	Yes	Yes	Yes	Yes
ECG	_	Yes	Yes	Yes	Yes	Yes
C-SSRS		Yes	Yes	Yes	Yes	Yes
YMRS	Yes	Yes	Yes	Yes	Yes	Yes
AIMS, BARS, and SAS ²		Yes	Yes	Yes	Yes	—

AE = adverse event; AIMS = Abnormal Involuntary Movement Scale; BARS = Barnes Akathisia Rating Scale; C-SSRS = Columbia Suicide Severity Rating Scale; ECG = electrocardiogram; SAS = Simpson-Angus Scale; YMRS = Young Mania Rating Scale.

¹ Descriptive statistics only.

² AIMS, BARS, and SAS assessments were added after implementation of Protocol Amendment 2.0.

Blinded data reviews will be conducted prior to unblinding the patients' treatment assignments for assessing the accuracy and completeness of the study database and defining analysis sets, patient evaluability, and appropriateness of the planned statistical methods.

9.1 Sample Size Considerations

The assumed effect size (treatment group difference relative to pooled SD) of 0.37 for lumateperone is based on a treatment difference of 3.3 units with a common pooled SD of 9 for the primary efficacy parameter, change from baseline to Day 43 in MADRS total score. A sample size of 350 patients (175 per treatment group) will need to be enrolled after the implementation of Amendment 2.0 (dated 02 Nov 2020) to provide 90% power for primary analysis for the combined population of Bipolar Disorder with mixed features and MDD with mixed features based on an MMRM model using simulation method (Lu, 2012). The simulation assumed a correlation of 0.7 between the repeated measures and a dropout rate of 10% based on historical data.

The assumed values of drop-out rate of 10%, correlation of 0.7, and standard deviation of 9 are approximate estimates from a previous successful study of lumateperone for bipolar depression. The assumed treatment difference of 3.3 used to obtain the power of 90% is considered appropriate as the generated sample size can cover a wide range of clinically relevant treatment difference to be detected as statistically significant.

The study will enroll approximately equal number of patients (175) for the Bipolar Disorder with mixed features and for MDD with mixed features following Amendment 2.0. Assuming an effect size of 0.45, and same assumptions of drop-out rate and correlation between the repeated measures, this sample size (approximately 87 patients in each treatment group) for each of the two subpopulations is expected to provide approximately 80% statistical power for the primary efficacy analysis with the adjustment of multiplicity for the testing of the primary analysis in each of the subpopulations.

The study randomized approximately 100 patients under the original protocol before the implementation of Amendment 2.0 (dated 02 Nov 2020); therefore, the total enrollment for the study will be approximately 450 patients.

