A statistical analysis plan (SAP) will be finalized prior to unblinding patients' treatment assignments.

Sample Size: The assumed effect size (treatment-group difference relative to pooled standard deviation) of 0.37 for lumateperone is based on a treatment difference of 3.3 units with a common pooled standard deviation of 9 for the primary efficacy parameter, change from baseline to Day 43 in MADRS total score. A sample size of 350 patients (175 per treatment group) enrolled after the implementation of Amendment 2.0 (dated 02 Nov 2020) will be needed to provide 90% power for primary analysis for the combined population of Bipolar Disorder with mixed features and MDD with mixed features based on a mixed-effect model for repeated measures (MMRM) using simulation method (Lu, 2012). The simulation assumes a correlation of 0.7 between the repeated measures and a dropout rate of 10% based on historical data.

The sample size and statistical power for the primary analyses in the subpopulations are presented in Section 9.1.

The study randomized approximately 100 patients under the original protocol before the implementation of Amendment 2.0 (dated 02 Nov 2020); therefore, the total enrollment for the study will be approximately 450 patients.

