3 STUDY OBJECTIVES

3.1 Primary Efficacy Objective

The primary objective of this study is to confirm the efficacy of lumateperone 42 mg administered orally once daily compared with that of placebo as measured by mean change from baseline to Day 43 in the MADRS total score in patients with bipolar depression with mixed features or MDD with mixed features.

This study will evaluate the efficacy of lumateperone 42 mg based on the following three sets of patients:

- 1. All patients enrolled after the implementation of Amendment 2.0, which includes all patients associated with Bipolar Depression with mixed features and all patients associated with MDD with mixed features;
- 2. All patients with Bipolar Disorder (I or II) with mixed features enrolled after the implementation of Amendment 2.0;
- 3. All patients associated with MDD with mixed features.

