9.4.4 Analysis of Primary and Key Secondary Efficacy Endpoints

The study is designed to evaluate the efficacy of lumateperone 42 mg based on the following primary and key secondary efficacy endpoints:

- Primary Endpoint Change from baseline to Day 43 in the MADRS total score.
- Key Secondary Endpoint Change from baseline to Day 43 in the CGI-S score.

The treatment effect on the primary efficacy endpoint will be evaluated in the combined population of Bipolar Disorder with mixed features and MDD with mixed features using a mixed-effect model for repeated measures (MMRM) method based on the mITT Set. The model will include the change from baseline at each pre-specified time point in the MADRS total score as the response variable; treatment group (lumateperone 42 mg and placebo), visit, site (or pooled site), the stratification factor at screening (Bipolar I, Bipolar II, or MDD), and treatment group-by-visit interaction as factors; and the baseline MADRS total score and visit-by-baseline MADRS total score interaction as covariates. An unstructured covariance matrix will be used to estimate the covariance among repeated measurements within patient. In the event the convergence cannot be attained with the unstructured correlation matrix, the following alternative structures will be attempted in the specified order: heterogeneous Toeplitz structure (TOEPH), heterogeneous

autoregressive(1) (ARH(1)), heterogeneous compound symmetry (CSH), No Diagonal Factor Analytic (FA0(q), with q equal to the number of time points), Toeplitz structure (TOEP), autoregressive(1) (AR(1)), and compound symmetry (CS). Model parameters will be estimated using restricted maximum likelihood. The Kenward-Roger approximation will be used to estimate the denominator degrees of freedom.

The MMRM method described above will also be used for the primary efficacy analyses based on the subpopulation of Bipolar Disorder with mixed features in the mITT Set and based on the subpopulation of MDD with mixed features in the mITT Set.

The key secondary efficacy endpoint, change from baseline to Day 43 in the CGI-S score, will be analyzed based on the mITT Set using an MMRM method similar to the one specified for the analysis of the primary efficacy endpoint, but replacing MADRS total score with CGI-S score for the baseline and baseline-by-visit interaction terms as covariates in the model.

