11. INTERIM ANALYSIS

No interim analysis is planned for this study.

12. SAMPLE SIZE CONSIDERATION

The sample size for this study is based on assumed effect size (treatment group difference relative to SD) of 0.37. This assumed effect size of 0.37 for lumateperone is based on a treatment difference of 3.3 units with a common pooled SD of 9 for the primary efficacy parameter, change from baseline to Day 43 in MADRS total score. A sample size of 350 patients (175 per treatment group) will be needed to be enrolled after Protocol Amendment 2.0 to provide 90% statistical power for primary analysis based on an MMRM using a simulation method (Lu 2012). The simulation assumed a correlation of 0.7 between the repeated measures and a dropout rate of 10% based on historical data.

13. STATISTICAL SOFTWARE

Statistical analyses of efficacy and safety parameters will be performed using version 9.4 of SAS.

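### Does Protocol 9.1 contradict itself by powering the combined population at an effect size of 0.37 and each of its two halves at 0.45?

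*Protocol*

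**What the plan says.** Protocol Section 9.1 starts from the combined population: "The assumed effect size (treatment group difference relative to pooled SD) of 0.37 for lumateperone" comes from a difference of 3.3 MADRS points and an SD of 9. With 175 patients per arm, a correlation of 0.7 between visits and 10% dropout, this is said to give 90% power. The section attributes the SD, correlation and dropout to an earlier lumateperone study and gives a reason for choosing 3.3.

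It then turns to the subpopulations: "The study will enroll approximately equal number of patients (175) for the Bipolar Disorder with mixed features and for MDD with mixed features". The power statement for each is conditional: "Assuming an effect size of 0.45, and same assumptions of drop-out rate and correlation between the repeated measures, this sample size", with about 87 per arm, "is expected to provide approximately 80% statistical power for the primary efficacy analysis with the adjustment of multiplicity". No source or difference in points is given for 0.45.

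The combined set is simply the two subpopulations together; Protocol Section 3.1 describes it as one "which includes all patients associated with Bipolar Depression with mixed features and all patients associated with MDD with mixed features". The synopsis gives only the 0.37 calculation and directs the reader onward: "The sample size and statistical power for the primary analyses in the subpopulations are presented in Section 9.1". SAP Section 12 likewise covers only the combined calculation: "The sample size for this study is based on assumed effect size (treatment group difference relative to SD) of 0.37".

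**The concern.** The combined population consists of two halves of equal planned size. With a common SD, its standardized effect is the average of the two subpopulation effects. An effect of 0.37 overall therefore cannot coexist with 0.45 in both halves: if one half were at 0.45, the other would have to be at 2 × 0.37 − 0.45 = 0.29. Section 9.1 nevertheless sets 90% and about 80% side by side, and no single scenario yields both.

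The subpopulation tests matter. Protocol Section 9.4.4 says the MMRM "will also be used for the primary efficacy analyses based on the subpopulation of Bipolar Disorder with mixed features in the mITT Set", and it treats MDD the same way. The synopsis also allows the key secondary endpoint (CGI-S) to be tested only after success in the combined population and in both subpopulations. A reader who took the about 80% as power under the effect that sized the trial would overrate each subpopulation test by about 20 points, and might later read a non-significant subpopulation result as stronger evidence against the drug than it is.

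**Working it through.** **Inputs.** From Protocol 9.1: difference 3.3, SD 9, 175 per arm combined, 87 per arm in each subpopulation, effect size 0.45 for the subpopulations, 10% dropout, correlation 0.7. From Protocol 9.4: two-sided alpha 0.05. From the synopsis: the combined test as gatekeeper, combined with Hochberg, taken here as Hochberg over the two subpopulations.

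**Assumptions of this check.** Equal SDs and equal true effects in the two halves. Dropout is handled in two ways: completers only (retention 0.90), or MMRM information with compound symmetry at 0.7, six visits and linear dropout (retention 0.957). Site terms are ignored.

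**Formulas.** With n effective patients per arm and effect d, the test statistic has mean m = d × √(n/2). Unadjusted power is u = Φ(m − 1.960), and power at alpha 0.025 is b = Φ(m − 2.241). Under Hochberg with two independent, equally powered tests, a subpopulation succeeds if its own p ≤ 0.025, or if its p lies between 0.025 and 0.05 and the other's is ≤ 0.05. Power for each is therefore b + (u − b) × u. The gate was added by simulation (3 million draws).

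**Step 1: the stated 90%.** d = 3.3/9 = 0.3667.
- n = 175 × 0.90 = 157.5: m = 3.254, power 90.2%.
- n = 175 × 0.957 = 167.5: m = 3.355, power 91.9%.

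The stated 90% reproduces.

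**Step 2: the stated 80%.** d = 0.45.
- n = 87 × 0.90 = 78.3: m = 2.816, u = 80.4%, b = 71.7%. Hochberg: 71.7 + (80.4 − 71.7) × 0.804 = 78.7%; with the gate, 78.5%.
- n = 87 × 0.957 = 83.2: m = 2.903, u = 82.7%, b = 74.6%. Hochberg: 81.3%; with the gate, 81.2%.

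The stated figure of about 80% reproduces, with the multiplicity adjustment included.

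**Step 3: the figure not printed.** d = 0.3667 in both halves.
- n = 78.3: m = 2.294, u = 63.1%, b = 52.1%. Hochberg: 52.1 + (63.1 − 52.1) × 0.631 = 59.0%; with the gate, 58.4%.
- n = 83.2: m = 2.366, u = 65.7%, b = 54.9%. Hochberg: 62.1%; with the gate, 61.5%.

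A t reference instead of the normal lowers the gated values by less than one point (57.8% and 60.9%). Without any adjustment each half would still have only 63–66%, so the shortfall from 80% does not depend on the multiplicity rule.

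**Step 4: the two scenarios in full (with gate and Hochberg).**

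| Effect in both halves | Combined | Each half | At least one | Both |
|---|---|---|---|---|
| 3.3/9 | 90–92% | 58–62% | 77–80% | 40–43% |
| 0.45 (4.05 points if the SD is 9) | 98% | 79–81% | 92–94% | 65–68% |

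The first row holds the 90% and the second the about 80%. They are different scenarios, and each printed figure is right in its own row.

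**The case for a change.** The strongest case for a change is that the effect that sized the trial is 0.37, the subpopulation tests are labelled primary, and the only subpopulation power in either document is quoted at a larger, unsupported effect. Two sentences would put this right at almost no cost, and they would warn readers that a non-significant subpopulation is quite likely even if the drug performs as planned.

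The arithmetic behind this stands: the gap is about 20 points, and no multiplicity rule or dropout assumption closes it. It also stands that 0.45 has no stated basis.

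The claim of a contradiction does not stand. Section 9.1 makes two conditional statements, each with its own disclosed input, and nowhere asserts that 0.37 overall and 0.45 in both halves hold together. The sample size is fixed by the combined test; the next paragraph then says what that fixed size delivers in each half at 0.45. Reporting the effect that a fixed sample detects with about 80% power is ordinary practice for a second layer of tests, and it needs no forecast behind it. The wording (an assumption, and power that is expected) does not say outright that this is meant, but it permits that reading. Section 9.1 also defends 3.3 on the ground that the resulting sample size covers a range of relevant differences, which presents it less as a best estimate than as one value in a range. SAP Section 12 loses nothing by leaving 0.45 out, because only the combined calculation sets the sample size.

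**Conclusion.** No change follows. The stated powers are correct on their stated inputs: 90–92% against 90% for the combined population at 3.3/9, and 79–81% against about 80% for each subpopulation at 0.45. What is missing is a reason for 0.45 and the subpopulation power at 3.3/9, which is about 58–62% in each half, with at least one success in about 77–80% of trials and both in about 40–43%. These figures assume equal true effects and SDs in the two diagnoses, 10% dropout, and Hochberg applied to the two subpopulations after the combined test; the sponsor's own simulation could move them by a point or two.

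Adding them to Section 9.1 would be explanation only. Planning power enters no estimate, p-value or type I error rate, and the sample size, the order of testing and the SAP would all stay the same. Anyone interpreting a non-significant subpopulation can work out the lower power from the inputs in 9.1, as above, and the confidence interval for that subpopulation will convey its precision directly.

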9.2 Planned Interim Analyses

No interim analysis is planned.

9.3 Analysis Sets

All Enrolled Set will contain all patients who signed the informed consent for the study.

All Patients Randomized Set will contain all patients who signed the informed consent and were randomized to study drug.

Intent-to-treat (ITT) Analysis Set will contain all randomized patients who received at least 1 dose of study drug and who had a non-missing (pre-dose) baseline assessment and at least 1 non-missing post-baseline assessment of MADRS total score.

Modified Intent-to-treat (mITT) Analysis Set will contain all randomized patients who received at least 1 dose of study drug and who had a valid (pre-dose) baseline assessment and at least 1 valid post-baseline assessment of MADRS total score and were enrolled after the implementation of Amendment 2.0 (dated 02 Nov 2020). Patients enrolled before the implementation of Amendment 2.0 will not be included in the mITT Analysis Set.

Sensitivity Set will contain all patients randomized after the implementation of Amendment 2.0 (dated 02 Nov 2020) and who received at least 1 dose of study drug and who had a valid (pre-dose) baseline assessment of MADRS total score. Patients enrolled before the implementation of Amendment 2.0 will not be included in the Sensitivity Set.

The Bipolar Intent-to-treat (bITT) Analysis Set will contain all randomized Bipolar Disorder patients who received at least 1 dose of study drug and had baseline assessment and at least 1 post-baseline assessment of MADRS total score. The bITT Analysis Set will be based on patients enrolled before the implementation of Amendment 2.0 as well as the patients of Bipolar Disorder with mixed features enrolled after the implementation of Amendment 2.0.Safety Analysis Set will contain all patients who received at least 1 dose of study drug.

